5.7.2. Subgroup Analyses of Efficacy Variables

The percent change in LDL-C from baseline over time will be summarized by the following subgroups of interest, assuming there are enough patients in each subgroup level to perform the evaluation:

- Gender (Female, Male)
- Geriatric (No: Age < 65, Yes: Age ≥ 65)
- Adolescent (Yes: Age < 18, No: Age ≥ 18)
- Race
- Ethnicity
- Baseline LDL-C (<130, ≥130 mg/dL)
- HoFH genotyping (homozygous, compound heterozygous, and double heterozygous)
- Receptor-negative mutation in both LDLR alleles (Yes, No)
- LDLR activity (null/null [LDLR activity ≤15%], not null/null [LDLR activity > 15%])
- Apheresis patients (Yes, No)

5.8. Analysis of Safety Data

Safety summaries for the study will be presented by patient group for the study in the safety analysis set, and again for the subpopulation of adolescent patients. No formal inferential testing will be performed. Summaries will be descriptive in nature.

All safety analyses will be performed using the baseline definitions described in Section 6.1.

General common rules

All safety analyses will be performed, unless otherwise specified, using the following common rules:

- Safety data in patients who do not belong to the safety analysis set (e.g., exposed but not enrolled) will be listed separately.
- The potentially clinically significant value (PCSV) values are defined as abnormal values considered medically important by the Sponsor according to predefined criteria/thresholds based on literature review and defined by the Sponsor for clinical laboratory tests and vital signs (PCSV version dated January 2009 [Appendix 10.4]).

Considering that the threshold defined in the PCSV list for monocytes and basophils can be below the ULN, the following PCSV criterion will be used for the PCSV analysis of monocytes and basophils:

- PCSV criterion for monocytes: >0.7 Giga/L or >ULN (if ULN ≥0.7 Giga/L).
- PCSV criterion for basophils: >0.1 Giga/L or >ULN (if ULN ≥0.1 Giga/L).

- PCSV criteria will determine which patients had at least 1 PCSV during the TEAE period, taking into account all evaluations including unscheduled or repeated evaluations.
- The treatment-emergent PCSV denominator by patient group for a given parameter will be based on the number of patients assessed for that given parameter at least once during the TEAE period.
- All measurements, scheduled or unscheduled, fasting or not fasting, will be assigned to Global Analysis Windows defined in Appendix 10.2 /Table 1 in order to provide an assessment for the screening visit through follow-up visit time points.
- For quantitative safety parameters including central laboratory measurements and vital sign scores, descriptive statistics will be used to summarize observed values and change from baseline values by visit.
- Open-label treatment period (OLTP): The treatment period used for quantitative analysis of laboratory and vital signs data in the open-label study period is defined from the day after the first dose of open-label study treatment to the day of the last dose of open-label study treatment + 28 days.
- Analyses performed according to diabetes status will be done considering diabetic patients as patients with either type 1 or type 2 diabetes in the medical history e-CRF page (regardless of the ongoing status).

5.8.1. Adverse Events

In general, the primary focus of AE reporting will be on TEAEs summarized in TEAE period. Post-treatment AEs will be summarized separately.

If an AE onset date (occurrence, worsening, or becoming serious) is incomplete, an imputation algorithm will be used to classify the AE as pre-treatment, treatment-emergent, or post-treatment. The algorithm for imputing date of onset will be conservative and will classify an AE as treatment-emergent unless there is definitive information to determine pre-treatment or post-treatment status. Details on classification of AEs with missing or partial onset dates are provided in Section 6.3.

Adverse event incidence tables will present the number (n) and percentage (%) of patients experiencing an AE by SOC and PT. In addition, incidence tables by SOC, HLG, HLT, and PT will be provided for all TEAEs, serious TEAEs, and TEAEs leading to permanent treatment discontinuation. Multiple occurrences of the same event in the same patient will be counted only once in the tables within a treatment phase (TEAE or post-treatment AE). For tables presenting by severity of events, the worst severity will be chosen for patients with multiple instances of the same event. The denominator for computation of percentages is the safety analysis set within each patient group, and again for the subpopulation of adolescent patients.

AE incidence tables will present data by SOC sorted alphabetically and PT sorted by decreasing frequency of the overall patient, and summarize the number (n) and percentage (%) of patients experiencing an AE.

The event rate per patient-year (the number of patients with an event divided by total patient-years) will be provided in the table for all TEAEs by SOC and PT. For a patient with an event, patient-year is censored at time of first event. For a patient without an event, patient-year corresponds to the length of the TEAE period.

Analysis of all treatment-emergent adverse events

The following TEAE summaries will be generated:

- Overview of TEAEs, summarizing number (%) of patients with any
 - TEAE;
 - Serious TEAE;
 - TEAE leading to death;
 - TEAE leading to permanent treatment discontinuation.
- All TEAEs by primary SOC, HLG, HLT, and PT
- All TEAEs by primary SOC and PT
- Number (%) of patients experiencing common TEAE(s) presented by primary SOC and PT (PT incidence $\geq 5\%$ in any patient group)
- All TEAEs relationship (related/not related) to evinacumab
- All TEAEs by maximum severity (i.e., mild, moderate or severe)
- A common TEAE related to any clinically significant signal will be further characterized as appropriate. The characterization of the clinically significant signal can include Kaplan-Meier curves for time from first dose to first occurrence of selected TEAE, time to resolution, and event duration. Patients without any event will be censored at the end of the respective TEAE period.

Analysis of all treatment emergent serious adverse event(s)

- All Serious TEAEs by primary SOC, HLG, HLT, and PT
- All Serious TEAEs by primary SOC and PT
- Patient listings of serious TEAEs will be provided in the report appendix.
- All Serious TEAEs relationship (related/not related) to evinacumab
- A serious TEAE related to any clinically significant signal will be further characterized as appropriate. The characterization of the clinically significant signal can include Kaplan-Meier curves for time from first dose to first occurrence of selected TEAE, time to resolution, and event duration. Patients without any event will be censored at the end of the respective TEAE period.

Analysis of all treatment-emergent adverse event(s) leading to treatment discontinuation

- All TEAEs leading to permanent treatment discontinuation, by primary SOC, HLG, HLT, and PT
- All TEAEs leading to permanent treatment discontinuation, by primary SOC and PT

- Patient listings of TEAEs leading to permanent treatment discontinuation will be provided in the report appendix.
- A TEAE leading to permanent treatment discontinuation and related to any clinically significant signal will be further characterized as appropriate. The characterization of the clinically significant signal can include Kaplan-Meier curves for time from first dose to first occurrence of selected TEAE, time to resolution, and event duration. Patients without any event will be censored at the end of the respective TEAE period.

Post-treatment adverse events

- All post-treatment AEs by primary SOC and PT
- All post-treatment SAEs by primary SOC and PT

Analysis of Cardiovascular events

- TEAEs suspected of being CV events by primary SOC and PT
- TEAEs suspected of being CV events categorized by adjudicated outcome of positive, negative, or in-process (as applicable)
- Number of patients with adjudication positive by outcome categories, specifically CHD death, non-fatal MI, fatal and non-fatal ischemic stroke, unstable angina requiring hospitalization, congestive heart failure requiring hospitalization, ischemia driven coronary revascularization procedure
- Patient listing of positively adjudicated TEAE CV events

Patient Deaths

The following summaries of deaths will be generated.

- Number (%) of patients who died by study period (TEAE and post-treatment) and reason for death;
- TEAEs leading to death (death as an outcome on the AE CRF page, as reported by the Investigator) by SOC and PT

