10.4.4.1. Adverse Events

Definitions

For safety variables, the following observation periods are defined:

- The pretreatment period is defined as the time from signing the ICF to before the first dose of study drug
- The open-label TEAE period is defined from the day of the first open-label study treatment administration to the day of the last open-label study treatment administration + 168 days
- The post-treatment period is defined as the time from the day after the end of the respective TEAE periods to the last study visit

Open-label TEAEs are defined as those events that developed, worsened, or became serious during the open-label TEAE period.

Analysis

All AEs reported in this study will be coded using the currently available version of the Medical Dictionary for Regulatory Activities (MedDRA®). Coding will be to lowest level terms. The verbatim text, the preferred term (PT), and the primary system organ class (SOC) will be listed.

Adverse event incidence tables will present data by SOC sorted alphabetically and PT sorted by decreasing frequency, and summarize the number (n) and percentage (%) of patients experiencing an AE. Multiple occurrences of the same event in the same patient will be counted only once in the tables. Data conventions for missing or partial AE dates will be addressed in the SAP. The denominator for computation of percentages is the respective SAF by the status of previous evinacumab treatment exposure, and again for the subpopulation of adolescent patients [yes/no].

Summaries of all TEAEs will at least include:

- All TEAEs (and patient listing)
- All treatment-emergent SAEs, including patient deaths (and patient listing)
- Treatment-emergent AESIs (eg, hypersensitivity and anaphylaxis, defined by a pre-specified grouping) (Section 9.4.3)
- TEAEs by severity (according to the grading scale outlined in Section 9.5.1), presented by SOC and PT, depicting the worse TEAE severity for those patients with multiple occurrences of the same event)
- All TEAEs leading to permanent treatment discontinuation (and patient listing)

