4.8.1.2. Adverse Events of Special Interest

Adverse events of special interest (AESI) are AEs (serious or non-serious) required to be monitored, documented, and managed in a pre-specified manner. AESIs will be recorded on the adverse event e-CRF using dedicated tick boxes, and/or identified using standard MedDRA queries (SMQ), company MedDRA queries (CMQ), MedDRA terms, and/or applicable laboratory assessments. Appendix 10.3 contains the definitions used to identify AESIs:

The AESIs include:

- Anaphylactic reactions (e-CRF)
- General allergic events (SMQ)
- Infusion reactions (e-CRF)
- Hepatic Disorder (SMQ, lab data)
- Pregnancy (e-CRF)
- Symptomatic overdose with investigational medicinal product (e-CRF)
- Neurocognitive events (CMQ)
- Neurologic events (e-CRF)
- New onset of diabetes (NOD) (lab data, MedDRA HLT, concomitant medications) for patients without diabetes mellitus at baseline
- Diabetic complication (CMQ, concomitant medications) for patients with diabetes mellitus at baseline
- Pancreatitis (e-CRF)
- Cataracts (MedDRA HLT)
- Immune complex diseases (SMQ)
- Muscle events/CK elevation (MedDRA SOC, SMQ, lab data)

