New onset of diabetes (NOD) for patients without diabetes mellitus at baseline	No	
No medical history of diabetes as specified in Cardiovascular History and Cardiovascular Risk Factors and Medical History CRF pages, AND Hb1Ac < 6.5% at baseline
 
AND one of the following:
 
Lab criteria: At least 2 values of HbA1c \geq6.5% during the TEAE period. NOTE: For patients with only a single measurement available during the TEAE period, a single value \geq6.5% will be considered and qualify the patient as NOD by default. For patients with several HbA1c measurements but only with the last one \geq6.5%, this single value \geq6.5% will be considered and qualify the patient as NOD by default.
 
OR
 
Lab criteria: At least 2 values of fasting glucose \geq126 mg/dL (7.0 mmol/L). NOTE: For patients with only a single measurement available during the TEAE period, a single value \geq126 mg/dL (7.0 mmol/L) will NOT be considered and will NOT qualify the patient as NOD. For patients with several fasting glucose measurements but only with the last one \geq126 mg/dL (7.0 mmol/L), this single value \geq 126 mg/dL (7.0 mmol/L) will NOT be considered and will NOT qualify the patient as NOD.
 
OR
 
HLT Diabetes mellitus (including subtypes)
 
OR
 
- Initiation of any new concomitant medication for hyperglycemia during the treatment period

Diabetic complication for patients with diabetes mellitus at baseline	No	For patients with medical history of diabetes as specified in Cardiovascular History and Cardiovascular Risk Factors and Medical History CRF pages, each of the following criteria will be considered, respectively:

AESI	Using an e-CRF specific tick box on AE page	Using Standard MedDRA Query (SMQ)/company MedDRA Query (CMQ) or lab data
		
 • Diabetes mellitus or diabetic complication TEAEs using HLTG Diabetic complications, HLT Diabetes mellitus (incl subtypes), and PTs Blood glucose increases, Glycosylated haemoglobin increased, Hyperglycaemia, Hyperglycaemic unconsciousness, and Hyperglycaemic seizure • Changes in diabetic medication dosage (specifically increases in dosage) or initiation of additional diabetic medication
Pancreatitis	Yes	No
Cataracts	No	HLT Cataract conditions
Immune complex diseases	No	SMQ (Narrow) Systemic lupus erythematosus SMQ (Narrow) Vasculitis SMQ (Narrow) Guillain-Barre syndrome

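### The only written AE denominator is the whole safety set, so by default the two diabetes AESIs are divided by patients who cannot have the event

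*SAP*

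**What the plan says.** SAP 5.8.1 gives a single rule for percentages in adverse event incidence tables: "The denominator for computation of percentages is the safety analysis set within each patient group", repeated for adolescents. Protocol 10.4.4.1 agrees: "The denominator for computation of percentages is the respective SAF by the status of previous evinacumab treatment exposure". Directly after that sentence, the protocol lists the summaries to be produced, and treatment-emergent AESIs are among them. SAP 1.2.3 records no departure from the protocol's statistical section. SAP 5.8.2 presents AESIs by system organ class and preferred term where that applies, and states no denominator.

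SAP 4.8.1.2 defines two AESIs on complementary subsets. One can arise only in patients who are already diabetic: "Diabetic complication (CMQ, concomitant medications) for patients with diabetes mellitus at baseline". Its counterpart can arise only in the remaining patients and is listed as follows: "New onset of diabetes (NOD) (lab data, MedDRA HLT, concomitant medications) for patients without diabetes mellitus at baseline".

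Table 2 in SAP 10.3 makes these conditions operational. New onset starts from "No medical history of diabetes as specified in Cardiovascular History" and the other listed CRF pages, together with a baseline HbA1c below 6.5%. The complication entry begins: "For patients with medical history of diabetes as specified in Cardiovascular History and Cardiovascular Risk Factors and Medical History CRF pages".

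SAP 5.8 adds a general rule that analyses by diabetes status are done "considering diabetic patients as patients with either type 1 or type 2 diabetes in the medical history e-CRF page". It does not say which analyses these are, and it sets no denominator.

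**The concern.** A patient without diabetes at baseline cannot be a case of diabetic complication under Table 2, and a patient with diabetes cannot be a case of new onset. If the written rule is followed, both kinds of patient still enter the denominator, as event-free.

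Safety is the primary endpoint and all reporting is descriptive, so the printed percentage is the result that readers will use. A complication percentage over all treated patients mixes two things: the risk among patients with diabetes, and how many such patients the group contains. It can look low only because the second is small. It also moves with the diabetes share of each group (Continue, New, adolescents) when the risk is the same.

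**Working it through.** **Inputs.** Planned enrolment is about 120, with about 14 adolescents (SAP 2.2). The two baseline conditions come from SAP 4.8.1.2 and Table 2, the denominator rule from SAP 5.8.1 and Protocol 10.4.4.1. The plan states no AESI rate and no diabetes prevalence, so there is no figure of its own to reproduce. The prevalence p is an assumption, shown over a range.

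**Can the diabetic subset exist?** Yes. Exclusion criterion 5 for evinacumab-naïve patients (Protocol 6.2.2) removes only newly diagnosed or poorly controlled diabetes. The list for patients from a previous evinacumab study (Protocol 6.2.3) has no diabetes criterion.

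**Formulas.** Let N be the group size and d = pN the number with diabetes at baseline.

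- Complication with k cases: k/N is printed and k/d is the at-risk percentage, so the ratio is N/d = 1/p. Because k cannot exceed d, the printed figure cannot exceed p.
- New onset with m cases: m/N is printed and m/(N-d) is the at-risk percentage, so the ratio is N/(N-d) = 1/(1-p).

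**Results for N = 120.**

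| Assumed p | d | Complication understated by | Highest printable complication % | New onset understated by |
|---|---|---|---|---|
| 5% | 6 | 20 | 5% | 1.05 |
| 10% | 12 | 10 | 10% | 1.11 |
| 15% | 18 | 6.7 | 15% | 1.18 |
| 20% | 24 | 5 | 20% | 1.25 |
| 30% | 36 | 3.3 | 30% | 1.43 |

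**Example at p = 10%.** Three complications print as 3/120 = 2.5%, against 3/12 = 25% of those at risk. Five new-onset cases print as 5/120 = 4.17%, against 5/108 = 4.63%.

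The new-onset column uses diabetes history alone. Table 2 also requires a baseline HbA1c below 6.5%, so the true at-risk set is N-d or smaller, and the factor is at least the one shown.

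**Group mix.** Suppose 25% of diabetics have a complication in two groups, one with p = 5% and one with p = 15%. The printed figures are 0.25 × 5% = 1.25% and 0.25 × 15% = 3.75%, a three-fold difference with equal risk.

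**Adolescents.** At p up to 20%, 14 adolescents include at most about 0.20 × 14 = 2.8 patients with diabetes. If there are none, the table prints 0/14 = 0% although nobody was at risk.

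**Does the general rule in SAP 5.8 settle it?** No. Besides setting no denominator, it takes diabetes from the medical history page. Table 2 also names the cardiovascular history and risk factor pages and, for new onset, baseline HbA1c. A numerator patient could fall outside a denominator built on the 5.8 definition. A patient with no history but a baseline HbA1c of 6.5% or more belongs to neither AESI, although SAP 4.1 plans a baseline category for exactly that range.

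**The case against.** The best counter-argument is that the SAP never expressly assigns the full safety set to these two AESIs. The sentence in 5.8.1 closes a paragraph on incidence tables by system organ class and preferred term. AESIs have their own section, which is silent. Some of the Table 2 criteria are laboratory values or medication changes that have no preferred term. The AESI labels name a subset, and the diabetes-status rule in 5.8 has no obvious use other than these two AESIs. A statistician might well program the at-risk denominator without being told. This much stands: a reader might infer that the SAP mandates the safety set for every AE percentage, these included, and the text does not go that far. What it supports is a default. The safety set is the only denominator written down, and the protocol places AESIs among the summaries that follow its rule. A programmer working from the documents would reach it.

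Second, part of the missing information is printed elsewhere. SAP 4.2 lists type 1 and type 2 diabetes as medical history of interest, and SAP 5.2 tabulates that history by group and for adolescents. A reader could divide the complication count by that number. This stands for complications, provided the CRF pages agree. The different page wording may be no more than loose drafting, since SAP 4.2 treats the cardiovascular pages as part of medical history. It does not work for new onset, because history and baseline HbA1c are listed as separate summaries and not cross-classified.

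Third, a percentage of all treated patients is a legitimate descriptive quantity, and nothing is tested. That is true, but it answers a different question from the one the AESI label poses.

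**Conclusion.** The point holds as a denominator that is not specified for two AESIs and whose written default misleads. The direction is certain if the default is applied: both percentages are too low, by 1/p for diabetic complication and 1/(1-p) for new onset.

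The size depends on a prevalence that the documents do not give. A reader might infer that the complication rate is necessarily diluted many-fold, or that few patients have diabetes. Neither can be shown from the documents. A factor of at least 3 needs p of one third or less. The new-onset effect is modest when p is low: 1.05 to 1.18 for p between 5% and 15%. Nor would every group difference be an artefact, only the part due to a different diabetes share.

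Event counts are unaffected and no inferential comparison depends on these figures. The SAP already uses a tailored denominator for potentially clinically significant values (patients assessed for the parameter, SAP 5.8), so the same principle here would be no novelty. The SAP should be corrected before database lock.

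**What to change.** In SAP 5.8.2, state that each diabetes AESI uses as denominator the safety-set patients in the group who meet its own Table 2 baseline condition, and print that number in the table:

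- Diabetic complication: a history of diabetes on the CRF pages that Table 2 lists.
- New onset of diabetes: no such history and a baseline HbA1c below 6.5%.

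A single history flag cannot serve both, because it leaves out the HbA1c part of the new-onset condition. Align the definition of diabetic patients in SAP 5.8 with the Table 2 pages. Say how patients with no history but a baseline HbA1c of 6.5% or more are classified, and report how many there are. Where nobody in a group is at risk, show the percentage as not applicable.

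The cost is a few lines of text and two denominator flags built from data already collected. The drawback is that the percentages will rest on small at-risk numbers, unstable among adolescents in particular, and may look less favourable. Printing the count with its at-risk number lets the reader judge that.
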